- Health care resource utilization and cost inputs were used from published observational studies that were published up to 10 years ago. Revising these estimates with updated RWE could impact the drugs' cost-effectiveness.

The objectives of this observational RWE study are focused on addressing these uncertainties and generating updated cost-effectiveness model inputs. The following research objectives will be addressed:

Primary Objective. Describe baseline demographic characteristics, attack rates, and attack-related medical service utilization among initiators of one of the three treatments for long-term prophylaxis use (Takhzyro, Haegarda, or Cinryze).

- What is the HAE baseline attack rate per month (stratified by severity) in the six months pre-initiation?
- Where is on-demand treatment for acute attacks administered? What is the distribution of specific drugs? How many prescriptions do patients receive?
- For patients with severe attacks, what percent end up hospitalized, and within these patients, what is the utilization of procedures such as cricothyrotomy/tracheotomy, intubation, and artificial respiration?
- What are the costs associated with medical utilization during the acute attack?

Exploratory Objective: Explore attack rates and utilization following long-term prophylaxis initiation.

- What is the severe attack rate per month, post-initiation?
- What percent of patients are attack-free during the follow up period?

- What are the utilization patterns of the prophylactic medications, post initiation?
- What percent of patients receive less frequent dosing for Takhzyro after six months attack free (in line with FDA recommendations)? Do any patients titrate down prior to six months?

5. Research methods

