5.2.1.4 HAE attack rates

Observational studies that evaluate attack rates in claims or EHR data sets are limited. There is currently no validated method to evaluate HAE attacks in claims data.

In creating our definitions of severe and non-severe attacks, we took guidance from clinical experts, treatment guidelines, and published literature that identified symptoms ([Longhurst & Bork 2019](#))⁵ or used diagnoses codes indicative of an attack (Tachdjian 2020).¹ Symptoms and diagnoses codes were cross referenced in a de novo code search to capture both ICD-9 and ICD-10 codes.

Attacks are defined by severity:

- **Severe attack:** Treatment guidelines and empirical data suggest that severe attacks are typically treated in the ED.⁶ For this analysis, severe attack will be defined in two ways: broadly as all-cause ED visits with or without hospitalization and more specifically as HAE ED visits with or without hospitalization. HAE specific severe attacks will be defined by a claim for an ED visit with or without hospitalization that includes diagnoses and drugs indicative of an attack (see Annex 2).
- **Non-severe attack-** Non-severe attacks are treated with on-demand therapy either by self-administration or administration by a healthcare professional. An attack treated by a healthcare professional will be defined as a medical service claim for an on-demand therapy occurring outside an inpatient or ED setting (e.g., physician office). For self-administration, we will estimate the number of attacks treated by calculating the number of doses dispensed based on dispensed quantity and approved dosages. Based on [treatment guidelines](#),⁶ patients should readily have on-demand therapy to treat two attacks, thus we will consider any doses dispensed over the two on-hand dosages of on-demand therapy as evidence of an attack.

Data on the duration of attacks by severity is limited, however attacks generally last between two and five days.⁷ Thus, on-demand therapy administrations by a healthcare professional, ED visits, and inpatient hospitalizations occurring within five days of each other will be considered part of a single attack. In cases where an on-demand therapy administration occurs within five days of an ED visit or hospitalization, the attack will be counted as a severe attack.

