5.2.1.7 Utilization

HAE and all-cause utilization will be estimated for the following:

- Number of home visits
- Number of office visits
- Number of ED visits
- Number of hospitalizations
- Pharmacy utilization
 - HAE on-demand therapy Rx's and total dose
 - HAE prophylaxis therapy Rx's and total dose, including proportion of days covered per label.
 - Other – number of Rx's

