Annex 2: Variable definitions and code lists

Treatment - Brand Name (Generic)	J Codes and NDCs	Source
Takhzyro (lanadelumab)	J0593 Injection, lanadelumab-flyo, 1 mg (code may be used for Medicare when drug administered under direct supervision of a physician, not for use when drug is self-administered) NDCs: 47783-0644-01	Clinical Pharmacology Database²⁰ and HCPCS²¹
Haegarda (C1 Inhibitor)	J0599 - Injection, HAEGARDA, 10 units (effective Jan 1, 2019) NDCs: 63833-0828-02 63833-0829-02	Clinical Pharmacology Database²⁰ and HCPCS²¹
Cinryze (C1 Inhibitor)	J0598 - Injection, C1 esterase inhibitor (human), 10 units NDCs: 42227-0081-01 42227-0081-05	Clinical Pharmacology Database²⁰ and HCPCS²¹
Ruconest (C1 Esterase Inhibitor, Recombinant)	J0596 - Ruconest, 10 units NDCs: 68012-0350-01 68012-0350-02 71274-0350-01 71274-0350-02	Clinical Pharmacology Database²⁰ and HCPCS²¹
Kalbitor (ecallantide)	J1290 - Injection, ecallantide, 1 mg NDCs: 47783-0101-01	Clinical Pharmacology Database²⁰ and HCPCS²¹
Berinert (C1 Inhibitor)	J0597 - Injection, C1 Esterase Inhibitor (Human), BERINERT, 10 units NDCs: 63833-0825-02	Clinical Pharmacology Database²⁰ and HCPCS²¹
Firazyr (icatibant)	J1744 - Injection, icatibant, 1 mg NDCs: 00093-3066-19	Clinical Pharmacology Database²⁰

	00093-3066-34 00093-3066-93 24201-0207-01 24201-0207-03 54092-0135-01 54092-0135-02 54092-0702-02 54092-0702-03 60505-6214-01 63323-0574-01 63323-0574-86 63323-0574-93 69097-0664-34 69097-0664-68	and HCPCS²¹
Orladeyo (berotralstat)	Newly approved drug (December 2020) and not available in the analysis data set which runs through March 31st 2020.	
Danazol (Danocrine)	NDCs: 00527-1368-01 00527-1369-01 00527-1369-06 00527-1392-01 00555-0633-02 00555-0634-02 00555-0635-02 00555-0635-09 42291-0243-01	Clinical Pharmacology Database²⁰
Cykokapron Lysteda (Tranexamic Acid)	NDCs: 00591-3720-30 55566-2100-01 55566-2110-02 60505-3638-01 60505-3638-03 66993-0090-30 66993-0121-30 69918-0301-30	Clinical Pharmacology Database²⁰
Amicar (Aminocaproic Acid)	NDCs: 17478-0447-08 17478-0768-30 17478-0769-30 49411-0050-30 49411-0051-30 49411-0052-08	Clinical Pharmacology Database²⁰

	52817-0815-08 60219-1637-03 60687-0505-25 62559-0225-30 66689-0330-08 69238-1596-08 69680-0115-30 69680-0116-30 72205-0049-30	
Oxandrin (Oxandrolone)	NDCs: 49884-0301-01 00185-0271-01 49884-0302-02 00185-0272-60	Clinical Pharmacology Database²⁰

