Android Methitest Testred Virilon (Methyltestosterone)	NDCs: 00187-0902-01 00115-1408-01 00187-0901-01 00115-7037-01	Clinical Pharmacology Database²⁰
Winstrol (Stanozolol)	NDCs: 0024-2253-04??	Clinical Pharmacology Database²⁰
Prophylactic use of Cinryze and Ruconest	Algorithm and code lists	Source
Cinryze prophylactic use	Cinryze is indicated for prophylaxis, but is used off-label for acute attacks. Prophylactic use will be defined as continuous refills of Cinryze averaging ≥ 1500 IU/week for ≥ 90 days.	Riedl 2018²²
Ruconest prophylactic use	Ruconest is indicated for on-demand use, but is used off-label for prophylaxis. Patients with Ruconest prophylactic use will be excluded from the cohort. Prophylaxis use will be defined as continuous refills of Ruconest averaging 50 IU/kg once weekly for 90 days.	Riedl 2018²²
every four-week	Used to determine if a dose reduction occurred.	

administration of Takhzyro	This will be measured over a 90-day follow-up period based on total dose <= 1200 mg over that period. The 1200 mg is based on three 300 mg injections plus one additional injection to account for potential variation in exact timing.	
Attack severity	Algorithm and code lists	Source
Severe	
ED visit with/without hospitalization, identified based on “Type of service” coded as inpatient or emergency room. Events identified as HAE-specific include at least one of the following diagnose (as a primary diagnosis for hospitalizations /or treatments indicative of an attack:
 
 € Codes often associated with HAE: ICD-9-CM 277.6 or ICD-10-CM D84.1 € Angioedema diagnosis: ICD-9-CM 995.1 or ICD-10-CM T78.3* € Administration of on-demand HAE treatment € Diagnosis of swelling, abdominal pain, or asphyxiation: 
 o ICD-9-CM 518.81, 518.84, 787.0*, 782.2, 789.0*, 786.02, 786.05, 786.1 o ICD-10-CM J96.0*, J96.2*, J96.9*, R06.0*, R06.1, R10.*, R11.*, R22.0*, R22.1, R19.0 	
UpToDate states severe attacks are treated in ED.²³
 
Tachdjian 2020¹
 
Zilberberg 2010²⁴
 
Longhurst & Bork, 2019

Non- severe attack	
Each dose of an on-demand therapy over two acute attack doses is considered an attack. The number of doses dispensed will be calculated from the quantity dispensed and recommended dose and
 
Any on-demand therapy administered outside an inpatient or emergency room setting will be considered a non-severe attack.
	
Utilization	Algorithm and code lists	Source

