cricothyrotomy/ tracheotomy	emergency tracheotomy (31603) and an emergency cricothyrotomy (31605)	
Dillon 2013²⁵
 
Esposito²⁶

intubation	The appearance of any of the following encounters CPT - 31500 ICD10 - 09HN7BZ, 0DH57BZ, 0DH58BZ, 0WHQ73Z, 0WHQ7YZ, 09HN8BZ, 0B21XEZ, 0BH13EZ, 0BH17EZ, 0BH18EZ, 0CHY7BZ, 0CHY8BZ ICD9 - 96.04, 96.7x, 96, 96.0,96.5	Pandya 2019²⁷ Singh 2020²⁸ De novo code look up
artificial respiration	The appearance of any of the following encounters Invasive mechanical ventilation: CPT - 94002, 94003, 94004, 94005, E0472, K0534 ICD10 - 5A1935Z, 5A1945Z, 5A1955Z noninvasive ventilation: CPT - 94660, A7027, A7034, A7044, E0452, E0470, E0471, E0601, K0183, K0193, K0194, K0532, K0533 ICD10 - 5A09459, 5A09557, 5A09357, 5A09358, 5A09359, 5A0935B, 5A09457, 5A09458, 5A0945B, 5A09558, 5A09559, 5A0955B ICD9 - 93.90 ventilation NOS: CPT- 94656, 94657 ICD10 - 5A0920Z, 5A0945Z, 5A0955Z, 5A19054, 5A0935Z, 5A09358, 5A0935B,	Pandya 2019²⁷ Singh 2020²⁸ Rosenthal 2020²⁹ De novo code look up
Costs	Algorithm and code lists	Source
Home nurse treatment	Standard cost amount for medical service claims with an on-demand drug administration where the place of service is ‘home’	
Physician office visit	Standard cost amount for medical service claims with an on-demand drug administration where the place of service is ‘office’	
ED visit	Standard cost amount for medical service claims where the type of service is coded as ‘emergency room, professional or facility’	
Hospitalization	Standard cost amount for medical service claims where the type of service is coded as ‘acute inpatient facility’	

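### The self versus professional split of non-severe attacks in Table 2 reflects how the on-demand drug was billed, not who gave it

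*Protocol*

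**What the plan says.** Section 4 places the question under the primary objective: "Where is on-demand treatment for acute attacks administered". Table 2 in Annex 3 reports the answer for non-severe attacks as self, home nurse and outpatient, beside prior base-case values of 64.9%, 13.8% and 21.3%.

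Two rules in Section 5.2.1.4 produce the split.

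- Professional: "An attack treated by a healthcare professional will be defined as a medical service claim for an on-demand therapy", outside the inpatient and ED settings.
- Self: "For self-administration, we will estimate the number of attacks treated by calculating the number of doses dispensed based on dispensed quantity and approved dosages". After a stock allowance, "we will consider any doses dispensed over the two on-hand dosages of on-demand therapy as evidence of an attack".

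Annex 2 repeats both. For dispensed drug, "Each dose of an on-demand therapy over two acute attack doses is considered an attack". The home and office cost definitions each begin "Standard cost amount for medical service claims with an on-demand drug administration where the place of service is" and then name the place of service. The code list for the on-demand drugs is headed "J Codes and NDCs". No visit or infusion code is listed for non-severe attacks.

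Section 5.2.1.7 separately asks for HAE and all-cause counts, including "Number of home visits".

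**The concern.** Under these rules the billing channel of the drug decides between self and professional. Place of service only divides the professional group into home and office. Nothing tests who gave a pharmacy-dispensed dose, nothing links a dispensed dose to a visit claim, and there is no row for unknown setting.

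Annex 1 lists Berinert and Ruconest as intravenous, so a patient could plausibly receive the drug from a pharmacy and have a nurse give it. If the visit claim then has no drug line, the attack goes into the self row. The visit also cannot be attached to the attack cost in Section 5.2.1.5, because the five-day linking rule covers professional administrations, ED visits and hospitalizations but not dispensed doses.

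Section 3 says the results will update inputs to the cost-effectiveness model. A self share that differs from 64.9% could be read as a change in practice when part of it comes from billing. The sensitivity analyses in Section 5.4.1.4 vary the five-day window and the two-dose stock, not the setting. The limitations in Section 5.4.1.5 say that attack algorithms are unvalidated but do not mention setting.

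**Working it through.** The protocol gives no figure for the size of this misclassification, so there is none to reproduce. The calculation illustrates its effect on the protocol's own comparator split.

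**Inputs (Annex 3, Table 2).** Self S = 64.9%, home nurse H = 13.8%, outpatient O = 21.3%; the sum is 100.0%. Base-case cost per home-nurse visit is $179. Base-case attack rate is 3.39 per month, or 6 × 3.39 = 20.34 in six months.

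**Assumed, not in the document.** p is the share of home-nurse attacks treated with pharmacy-dispensed drug and no drug line on the visit claim. It is varied from 0 to 100%.

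**Step 1: no stock deduction.** This corresponds to the planned sensitivity analysis. Reported self = S + pH. Reported home nurse = H(1 − p). Visit cost lost per non-severe attack = 0.138 × p × $179.

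| p | Self | Home nurse | Outpatient | Cost lost |
|---|---|---|---|---|
| 0 | 64.9% | 13.8% | 21.3% | $0 |
| 25% | 64.9 + 3.45 = 68.35, about 68.4% | 10.35, about 10.4% | 21.3% | about $6 |
| 50% | 64.9 + 6.9 = 71.8% | 6.9% | 21.3% | about $12 |
| 100% | 64.9 + 13.8 = 78.7% | 0% | 21.3% | about $25 |

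If a share g of outpatient doses takes the same route, gO is added to self. With p = 50% and g = 25%, self is 64.9 + 6.9 + 5.3 = 77.1%, home nurse 6.9% and outpatient 16.0%.

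**Step 2: with the two-dose deduction.** Suppose patients already held stock when baseline began, so the two subtracted doses were in fact used. Let N be the attacks in six months, all treated as non-severe. Reported self = (SN + pHN − 2)/(N − 2). At N = 20.34, SN = 13.20 and HN = 2.81.

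- p = 0: (13.20 − 2)/18.34 = 61.1%
- p = 25%: (13.20 + 0.70 − 2)/18.34 = 64.9%, no net shift
- p = 50%: (13.20 + 1.40 − 2)/18.34 = 68.7%
- p = 100%: (13.20 + 2.81 − 2)/18.34 = 76.4%

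**Step 3: break-even.** Setting reported self equal to S gives p = 2(1 − S)/(HN) = 0.702/(0.138N).

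- 3.39 attacks per month (N = 20.34): p = 25%
- 2 per month (N = 12): p = 42%
- 1 per month (N = 6): p = 85%

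Below these values the net error is away from self; above them it is toward self. If the two doses do remain unused, the deduction is correct, there is no offset, and the Step 1 figures apply.

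**The case against.** A reader might infer that the reported split will be biased toward self. The documents do not support that as a net statement. The two-dose deduction comes off the self count alone and can cancel or reverse the shift (Steps 2 and 3). This objection stands. It does not validate the split, though: two opposing errors of unknown size do not make a measurement, and the planned analysis without the deduction removes the offset.

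A reader might also infer that such a visit disappears altogether. It does not. Sections 5.2.1.6 and 5.2.1.7 include all-cause home-visit costs and counts, so it still appears there. Only the setting split and the attack-linked cost miss it. Mean cost per captured visit changes only if the missed visits cost something different.

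The premise about billing is not in the document. The Annex 2 wording on drug administration does not expressly require the drug to be billed on the visit claim. But only J codes and NDCs are given to find it, so the plan offers no other route. The intravenous example does not cover the whole on-demand mix: Firazyr and Kalbitor are subcutaneous and together make up 50% of the Table 2 assumption.

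The money is small, at most about $25 per non-severe attack in Step 1, against $1,796 per ED visit and $5,782 per hospitalization. The mechanism relabels a dose already counted as an attack, so it does not by itself move the total attack rate. A claim that it changes the benefit credited to prophylaxis would need the model, which is not supplied; Section 5.4.1.5 refers the use of attack estimates to a separate Model Analysis Plan.

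Finally, using visit diagnoses as the primary rule would capture routine visits and could add attacks. Section 5.1.1.2 itself notes that HAE has no specific diagnosis codes. That is a good reason not to replace the primary rule.

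**Conclusion.** The point holds as one of measurement and labelling. The self row counts pharmacy-dispensed doses, and the plan has no means of telling who gave them. For a dispensed dose given by a professional without a drug line on the visit claim, the error can run only toward self, and the visit cost is lost from the attack-linked cost.

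The size is unknown. The 68.4%, 71.8% and 78.7% figures are illustrations that assume p = 25%, 50% and 100%, the Table 2 comparator as the true split, no outpatient doses affected, and no stock deduction. With the deduction and prior stock, the net direction depends on p and on the attack rate. The point deserves correction because setting is a question under the primary objective, is set directly against base-case model inputs, and is covered by no limitation or sensitivity analysis.

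**What to change.** 1. Keep the current rule as primary. Rename the self row in Table 2 'pharmacy-dispensed (presumed self)', and state in Section 5.4.1.5 that setting may be misclassified.
2. Add a sensitivity analysis to Section 5.4.1.4. Reassign already counted dispensed doses to home or office when a home or office visit claim with an Annex 2 HAE or angioedema diagnosis (277.6/D84.1, 995.1/T78.3*) follows a dispensing. Apply the five-day episode rule so that clustered visits move one dose. Cap the reassignment at the number of counted dispensed doses, so the total attack rate is unchanged. Include the costs of those visits in the attack cost.
3. Report the split under both rules, each with and without the two-dose deduction, as a range.

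The cost is some extra programming; home and office visits are already extracted for Section 5.2.1.7, and no new data source is needed. The drawback is that some routine visits will be reassigned, so the visit-based result is only a rough upper limit on professional administration and should be labelled as such.

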5.4.1.4 Sensitivity analyses

We will conduct sensitivity analyses around attack definitions including:

- In our definition of attacks, we considered on-demand therapy administrations by a healthcare professional, ED visits, and inpatient hospitalizations occurring within *five*

days of each other to be considered part of a single attack. We will vary this duration in sensitivity analysis to determine how this impacts attack rates.

- In our definition of non-severe attacks, we assume that patients will have on-demand treatment on hand to treat up to 2 attacks, which is based on treatment guideline recommendations. In sensitivity analysis, we will estimate the number of attacks treated by self-administration without subtracting out two doses to represent drug on-hand.

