Annex 1: HAE drugs

Generic	Brand (Administration)	Acute Attack Dose	Long-Term Prophylaxis Dose	How Supplied
C1 Inhibitor, Human (plasma derived C1 inhibitor [pdC1INH])	Cinryze* (IV)	Adults† 1,000 units once. Additional 1,000 units IV if no improvement 60 minutes after first dose. (not studied in children)	Adults & Children ≥12 years 1,000 units every 3-4 days Max Dose: 2,500 units or 100 units/kg every 3 days Children (6-11 years) 500 units every 3-4 days Max Dose: 1,000 units every 3 days Short-Term Prophylaxis† (before a procedure) 20 units/kg or 1,000 units immediately prior to procedure	Cinryze 500 units Powder Vial Reconstitute with 5mL SWFI Concentration: 100 units/mL
	Haegarda* (SC)		Adults & Children ≥6 years 60 IU/kg twice weekly (every 3-4 days)	Haegarda 2000 IU Powder Vial Reconstitute with 4mL SWFI Concentration: 500 IU/mL Haegarda 3000 IU Powder Vial Reconstitute with 6mL SWFI Concentration: 500 IU/mL
	Berinert* (IV)	Adults & Children ≥6 year 20 IU/kg once		Berinert 500 IU Power Vial Reconstitute with 10mL SWFI Concentration: 50 IU/mL

Generic	Brand (Administration)	Acute Attack Dose	Long-Term Prophylaxis Dose	How Supplied
Lanadelumab	Takhzyro* (SC)		Adults & Children ≥12 years 300mg every 2 weeks. After 6 months, reduce to every 4-week dosing if patient well-controlled.	Takhzyro 300mg/2mL Solution Vial Concentration: 150mg/mL
C1 Esterase Inhibitor, Recombinant (recombinant human C1 inhibitor [rhC1INH])	Ruconest* (IV)	Adults & Children ≥13 years (non-laryngeal attacks) 50 IU/kg/dose Max Dose: 4,200 IU/dose; 8400 IU per 24 hours	Adults & Children ≥13 years† 50 IU/kg/dose once or twice weekly Max Dose: 4,200 IU/dose once or twice weekly Short-Term Prophylaxis† (before a procedure) 50 IU/kg or 1,000 units immediately prior to procedure	Ruconest 2100 IU Powder Vial Reconstitute with 14mL SWFI Concentration: 150 IU/mL
Ecallantide	Kalbitor* (SC)	Adults & Children ≥12 years 30mg once (administered as three injections of 10mg) Max Dose: 60mg in 24 hours		Kalbitor 10mg/mL Vial Solution for Injection (3 vials per package)
Icatibant	Firazyr (SC)	Adults 30mg once. Repeat administrations in 6-hour intervals. Max Dose: 90mg in 24 hours (EU Pediatric Dosing Weight Based)		Firazyr 30mg/3mL Solution Vial Icatibant 30mg/3mL Solution Prefilled Syringe
Berotrastat	Orladeyo* (Oral)		Adults & Children ≥12 years 150 mg once daily. Adjustment: 110mg once daily for hepatic impairment or GI reactions.	Orladeyo 110mg Capsule Orladeyo 150mg Capsule

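### Each dispensed on-demand dose above two counts as one attack, so re-dosed attacks are counted two or three times, and no planned analysis bounds the rate from below

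*Protocol*

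**What the plan says.** Protocol section 5.2.1.4 splits non-severe attacks in two. Treatment by a professional is "defined as a medical service claim for an on-demand therapy occurring outside an inpatient or ED setting". Self-treated attacks have no claim of their own and are estimated by "calculating the number of doses dispensed based on dispensed quantity and approved dosages". From that total, "we will consider any doses dispensed over the two on-hand dosages of on-demand therapy as evidence of an attack". Annex 2 (non-severe attack) fixes the ratio: "Each dose of an on-demand therapy over two acute attack doses is considered an attack".

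The merging rule in section 5.2.1.4 reads that "on-demand therapy administrations by a healthcare professional, ED visits, and inpatient hospitalizations occurring within five days of each other will be considered part" of one attack. It goes on to say that where "an on-demand therapy administration occurs within five days of an ED visit or hospitalization, the attack will be counted as a severe attack". Dispensed doses are not in the list.

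Annex 1 allows more than one dose in an acute episode. The icatibant entry reads "30mg once. Repeat administrations in 6-hour intervals. Max Dose: 90mg in 24 hours". Ecallantide is 30 mg with a maximum of 60 mg in 24 hours. Ruconest has a maximum of 4,200 IU per dose and 8,400 IU per 24 hours.

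Section 5.4.1.4 plans two sensitivity analyses. One varies the five-day window. The other reruns the self-administered count "without subtracting out two doses to represent drug on-hand".

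**The concern.** The rule assumes one dose per attack, and the Protocol's own dosing table does not. The merging rule cannot repair this. It works on dated events, and a count built from dispensed quantity has no date of use to link to another dose or to an ED visit. The same assumption sits inside the deduction, where drug to treat two attacks is taken to be two doses.

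The count feeds the primary output. Section 5.4.1.1 divides total attacks by person-months, and Annex 3 Table 2 reports HAE-specific severe and non-severe attacks as one mean monthly rate, beside the severity split and the self, home and outpatient split. Section 4 of the Protocol itself notes that small changes in attack frequency could substantially alter the cost-effectiveness results.

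**Working it through.** The Protocol gives no expected count or sample size for this rate, so there is no planned figure to reproduce. The check applies the counting rule to a known number of attacks.

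**Inputs from the Protocol**
- Doses per 24 hours (Annex 1): icatibant 90/30 = 3; ecallantide 60/30 = 2; Ruconest 8,400/4,200 = 2.
- Reference rate 3.39 per month (Annex 3 Table 2): 3.39 × 6 = 20.34 attacks in baseline.
- Low rate, one attack per four weeks (Annex 4, Takhzyro coverage): 180/28 = 6.43 attacks, or 1.07 per month.
- Site split of non-severe attacks (Annex 3 Table 2): self 64.9%, home nurse 13.8%, outpatient 21.3%.

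**Assumed, not in the documents**
- 10% of attacks are severe (30% as an alternative).
- 10% or 30% of self-treated attacks take one extra dose.
- Each dose used is replaced by a fill within baseline, so the patient was already stocked.

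**Formula**

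Counted rate = [severe + professionally treated + max(0, dispensed doses − 2)] / 6. The planned sensitivity analysis replaces the 2 by 0.

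**Step 1: the deduction alone, no re-dosing.** At 3.39 per month it removes 2/20.34 = 10%, giving (20.34 − 2)/6 = 3.06. At one per four weeks it removes 2/6.43 = 31%, giving 0.74 against 1.07.

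**Step 2: 30% re-dosed once, 10% severe, true rate 3.39.**
- Severe: 0.10 × 20.34 = 2.03. Non-severe: 18.31.
- Self-treated: 0.649 × 18.31 = 11.88. Professionally treated: 6.43.
- Dispensed doses: 11.88 × 1.3 = 15.44.
- Primary: (2.03 + 6.43 + 13.44)/6 = 3.65 (+8%).
- Without the deduction: (2.03 + 6.43 + 15.44)/6 = 3.98 (+18%).
- Self-treated share of non-severe attacks: 13.44/19.87 = 67.7%, or 15.44/21.87 = 70.6% without the deduction, against a true 64.9%.

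**Step 3: how far this depends on the assumptions.**

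| True rate | Severe | Re-dosed once | Primary | No deduction |
|---|---|---|---|---|
| 3.39 | 10% | 10% | 3.25 | 3.59 |
| 3.39 | 10% | 30% | 3.65 | 3.98 |
| 3.39 | 30% | 30% | 3.52 | 3.85 |
| 1.07 | 10% | 30% | 0.93 | 1.26 |

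The deduction absorbs two surplus doses. At 3.39 per month with 10% severe, that is 2/11.88 = 17% of self-treated attacks re-dosed once. Above that share both planned results exceed the truth; below it they lie on either side.

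**Step 4: ED overlap.** If half of the 2.03 severe attacks were preceded by a dispensed dose (assumed), that adds 1.02 attacks in six months, or 0.17 per month.

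**The case against.** The strongest defence is that the rule is a disclosed approximation. Section 5.2.1.4 and section 5.4.1.5 both say that no validated claims algorithm exists, and the latter refers use of the estimates to a Model Analysis Plan that is not at hand. The deduction also offsets surplus doses. At one attack per four weeks the primary rule still undercounts with 30% re-dosed (0.93 against 1.07). For a stocked patient who never re-doses, the planned rerun without the deduction is already the right count. No re-dosing share is documented, and a 24-hour maximum is not typical use.

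All of that stands, and it limits the point. It does not remove it: the disclosure does not change how doses are grouped, and neither planned analysis groups them.

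A reader might infer four stronger things that the documents do not support:
- **That the rate is biased upward overall.** The deduction works the other way, so the sign depends on the attack rate, stock and re-dosing.
- **That nurse-treated attacks are routinely counted twice.** Such an attack counts only if its medical claim carries the on-demand drug. Duplication would also need a pharmacy fill used for the same attack.
- **That whole-vial dispensing inflates weight-based products.** This needs units to be divided by the per-kg dose without rounding, and the text does not state the conversion.
- **That an ED or inpatient claim without a drug line shows a home dose was used.** Section 5.3.1.2 says that drugs used during hospital stays are not recorded, so a missing line on an admission is expected.

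**Conclusion.** The point holds in limited form. Multiple counting of re-dosed attacks follows directly from section 5.2.1.4 and Annex 2 read against Annex 1, for any patient with more than two dispensed doses. ED duplication is possible but conditional on a dispensed dose being used in the same attack. The net error can have either sign: with one extra dose in 0 to 30% of self-treated attacks and 10% severe, the primary result runs from −10% to +8% at 3.39 per month and from −31% to −14% at 1.07. These sizes are illustrations that rest on assumed shares.

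The firm defect is that the only planned sensitivity analysis of this count moves it upward, so the reported pair of results need not contain the true rate. Because use of the estimates is governed by a document not at hand, the effect on the cost-effectiveness result cannot be judged here. This is a cheap and worthwhile improvement rather than an error that invalidates the study.

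**What to change.** 1. In section 5.4.1.4, add a sensitivity analysis that divides dispensed doses by a stated range of doses per attack, from 1 up to the Annex 1 24-hour maximum for each product. The maximum serves as an extreme lower bound for counting only and implies nothing about treatment. State whether the deduction is taken before or after the division. In the step 2 example, without the deduction, dividing by 1 gives 3.98, by 1.3 gives 3.39 (the truth there), and by 3 gives (2.03 + 6.43 + 15.44/3)/6 = 2.27, so the truth is bracketed.
2. In section 5.2.1.4 and Annex 2, apply the two-dose deduction only to patients with no on-demand fill before day −180, where look-back exists. Keep the current rule for the others.
3. As a sensitivity analysis only, in patients with earlier on-demand fills, do not count one dispensed dose per ED-treated attack as a separate attack. Do not use a missing drug line as evidence of home dosing.

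The cost is revised wording and a few more runs on the same data. Only 180 days of prior enrollment are required, so look-back will be incomplete for some patients. The reported range for the attack rate will be wider.

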5.4 Statistical analysis

5.4.1.1 Baseline attack rates (primary objective)

Attack rates will be calculated as the total number of attacks in the cohort divided by the number of person-months during baseline (six months prior to initiation of prophylaxis treatment). The rates

and percentages of attacks by severity (severe all-cause, severe-HAE specific, non-severe) will also be calculated for the baseline cohort.

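### The five-day merge cannot absorb self-administered doses, so an attack treated at home with a dose above the two-dose allowance and then seen in the ED counts once as non-severe and once as severe

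*Protocol*

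**What the plan says.** Attacks come from two kinds of record.

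- **Severe attacks** are dated claims, defined "broadly as all-cause ED visits with or without hospitalization and more specifically as HAE ED visits with or without hospitalization" (5.2.1.4).
- **Self-treated non-severe attacks** are a quantity: "we will estimate the number of attacks treated by calculating the number of doses dispensed based on dispensed quantity and approved dosages". Two doses are treated as stock, and "we will consider any doses dispensed over the two on-hand dosages of on-demand therapy as evidence of an attack". Annex 2 gives the same rule: "Each dose of an on-demand therapy over two acute attack doses is considered an attack".

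The rule that joins events into one attack covers "on-demand therapy administrations by a healthcare professional, ED visits, and inpatient hospitalizations occurring within five days of each other". Section 5.4.1.4 repeats these three event types when it describes varying the window. A further sentence in 5.2.1.4 deals with severity; cut one word short, it reads: "In cases where an on-demand therapy administration occurs within five days of an ED visit or hospitalization, the attack will be counted as a severe".

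For the result, section 5.4.1.1 states: "Attack rates will be calculated as the total number of attacks in the cohort divided by the number of person-months during baseline". The first row of Table 2 in Annex 3 combines HAE-specific severe and non-severe attacks in one monthly rate and sets it beside a prior base case of 3.39.

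**The concern.** A patient who injects at home, does not settle and goes to the ED has had one attack. The records show a dispensed dose and an ED claim. The merge does not list self-administration, and could not use it, because a pharmacy fill shows supply and not the day of use. If the dose lies above the allowance, it enters the non-severe count while the visit enters the severe count, and the two are added.

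The primary objective asks for the baseline attack rate by severity. Section 4 says that the earlier cost-effectiveness results could change substantially with small shifts in assumptions such as attack frequency. The overlap acts on the total rate, the non-severe rate, the severity split and the self-treated row of Table 2. Neither planned sensitivity analysis isolates it. One varies the window for the same three event types. The other drops the two-dose subtraction, which adds self-treated attacks.

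**Working it through.** The protocol states no figure for this overlap, so there is none to reproduce. The check applies the counting rule as written and then scales it.

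**Rule (5.2.1.4, Annex 2, 5.4.1.1).** Self-treated non-severe = max(0, doses dispensed − 2). Severe = merged ED or inpatient episodes. Total = sum.

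**One true attack: one home dose, then the ED**

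- 1 or 2 doses dispensed: 0 + 1 = 1. No double count.
- 3 doses dispensed (2 stock, 1 used): 1 + 1 = 2. Double count.
- 1 dose dispensed, sensitivity analysis without subtraction: 1 + 1 = 2. Double count.

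**Four true attacks: three settled at home, one treated at home and then seen in the ED**

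- *Stock bought within baseline* (6 dispensed, 2 kept, 4 used). Main: (6 − 2) + 1 = 5, against 4 true.
- *Stock already held at the start of baseline* (an assumption; 4 dispensed). Main: (4 − 2) + 1 = 3, against 4 true. Without subtraction: 4 + 1 = 5.

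The overlap is present in both cases, but the main total is too high in the first and too low in the second.

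**Scaling.** Let s be the true severe share and f the fraction of severe attacks first self-treated from home supply, one dose each. The protocol gives neither; both are assumed. If every such dose lies above the allowance and all else is counted correctly:

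- counted total / true total = 1 + s·f
- counted severe share = s / (1 + s·f)

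Each cell shows the addition to the total, then the severe share as it would be reported.

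| s | f = 25% | f = 50% | f = 75% |
|---|---|---|---|
| 5% | +1.25%, 4.9% | +2.5%, 4.9% | +3.75%, 4.8% |
| 10% | +2.5%, 9.8% | +5%, 9.5% | +7.5%, 9.3% |
| 20% | +5%, 19.0% | +10%, 18.2% | +15%, 17.4% |

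For example, 0.20 × 0.75 = 0.15, and 0.20 / 1.15 = 17.4%. Purely for scale, a true rate equal to the prior base case would be counted as 3.39 × 1.0125 = 3.43 to 3.39 × 1.15 = 3.90 per month from this component alone. Doses that fall within the allowance are not counted, so s·f is a ceiling for the component.

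**The case against.** **The severity sentence already covers it.** That sentence speaks of an on-demand administration without limiting it to professionals, so the authors may have meant a home dose followed by an ED visit to be one severe attack. As a statement of intent this is fair. It cannot be carried out for self-administration, because the protocol defines no date for it.

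**The effect is conditional.** This stands. In the main analysis only doses above two are counted, so a reader who infers that every home-treated attack reaching the ED is counted twice goes too far.

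**The total may not be too high.** This also stands. A reader might infer that the planned baseline rate is inflated overall. The second four-attack case shows the opposite net result, because two doses are subtracted from a patient who already held them. In that case the planned main and no-subtraction results (3 and 5) straddle the true 4, but not by design and not in general.

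**The uncertainty is disclosed.** Sections 5.2.1.4 and 5.4.1.5 say that no validated claims algorithm exists, and 5.4.1.5 refers to a Model Analysis Plan for how attack estimates are used. That plan is not at hand, so the effect on the model cannot be judged here. The general caveat names neither this overlap nor its direction.

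**Conclusion.** The concern holds as a conditional double count fixed by the protocol's own definitions. It arises when a counted home dose and an ED or inpatient claim belong to the same attack. Taken alone, it overstates the non-severe count and the total and lowers the severe share through its denominator. The severe count and severe rate do not move, so the documents do not support reading the severe rate itself as biased by this. Patients with two or fewer dispensed doses are affected only in the sensitivity analysis without subtraction.

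The size is not known. The ceiling of 1.25% to 15% rests wholly on the assumed ranges for s and f and on one dose per attack. The sign of the net error in the total is undetermined. This justifies an added bounding analysis; it does not call for replacing the primary definition.

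**What to change.** Add one sensitivity analysis to 5.4.1.4, run both with and without the two-dose subtraction:

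- For each HAE-specific severe attack in a patient with an earlier on-demand pharmacy fill, deduct one counted dispensed dose, not below zero. The all-cause definition should not be used here, because it would remove doses for unrelated ED visits.
- For ED-only attacks, skip the deduction if an on-demand drug appears on the ED claim.
- For admissions, deduct regardless. Section 5.3.1.2 says that inpatient drug use is not recorded, so a missing drug claim says nothing about where the dose came from.

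Report the total rate, non-severe rate and severity split beside the planned results, labelled as an outer bound, and name the overlap in 5.4.1.5.

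Both versions are needed. In the four-attack example with stock bought in baseline, the deduction under subtraction gives (6 − 2 − 1) + 1 = 4, which is correct. With stock already held, it gives (4 − 2 − 1) + 1 = 2 under subtraction and (4 − 1) + 1 = 4 without it.

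The cost is a few added result rows from data already held. The downside is over-correction wherever the home supply was not used.
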